3.1 Inclusion Criteria

Informed Consent

- ___ 1. Documented informed consent of the participant and/or legally authorized representative.
 - Assent, when appropriate, will be obtained per institutional guidelines

Age Criteria, Performance status

- ___ 2. Age: ≥ 18 years
- ___ 3. Patients must have a life expectancy of > 3 months
- ___ 4. ECOG ≤ 2

Nature of Illness and Illness Related Criteria

- ___ 5. Patients must have a diagnosis of cutaneous CD30+LYPD
- ___ 6. Patients must be relapsed or are refractory to at least 1 prior line of therapy
- ___ 7. At least 2 weeks from prior therapy to time of start of treatment. Prior therapy includes steroids (except prednisone or equivalent – up to 10 mg/day is allowed).

Clinical Laboratory and Organ Function Criteria (To be performed within 21 days prior to Day 1 of protocol therapy unless otherwise stated [see Section 10.0])

 ___ 8. ANC $\geq 1000/\text{mm}^3$ NOTE: Growth factor is not permitted within 14 days of ANC assessment unless cytopenia is secondary to disease involvement. 	ANC: 	Date:

 ___ 9. Platelets $\geq 50,000/\text{mm}^3$ NOTE: Platelet transfusions are not permitted within 14 days of platelet assessment unless cytopenia is secondary to disease involvement. 	Plts: 	Date:

 ___ 10. ___ 10. Total bilirubin $\leq 1.5 \times \text{ULN}$ (unless has Gilbert's disease) 	ULN: Bil: 	Date:

 ___ 11. AST $\leq 2.0 \times \text{ULN}$ 	ULN: AST: 	Date:

 ___ 12. ALT $\leq 2.0 \times \text{ULN}$ 	ULN: ALT: 	Date:

 ___ 13. Creatinine clearance of $\geq 30 \text{ mL/min}$ per 24 hour urine test or the Cockcroft-Gault formula or $\text{CrCl (mL/min)} = \frac{(140-\text{age}) \times \text{actual body weight (kg)}}{72 \times \text{serum creatinine (mg/dL)}} \times 0.85 \text{ for females}$ 
Or
 $\text{CrCl (mL/min)} = \frac{(140-\text{age}) \times \text{actual body weight (kg)}}{0.8136 \times \text{serum creatinine (umol/L)}} \times 0.85 \text{ for females}$ 	Serum Cr: Cr Clearance: 	Date:

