7.0 DOSE DELAY/MODIFICATION GUIDELINES

7.1 Dose Modifications for Leflunomide

7.1.1 General Information

- a. The study will use the NCI Common Terminology Criteria for Adverse Events (CTCAE) version 5.0 to grade toxicities. A copy of the version 5.0 can be downloaded from:
<http://evs.nci.nih.gov/ftp1/CTCAE/About.html>
- b. Rules for dose modification are found in Table 7.1.1.
- c. Baseline values are from the last values obtained prior to treatment.
- d. **For holds due to toxicities related to study agent, if the participant does not meet criteria to resume treatment within 14 days, the participant must permanently discontinue study treatment.**

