Diarrhea Grade 4 (≥10 stools/day > baseline)	
At 20 mg:
 
Hold study agent and provide optimal anti-diarrheal therapy.
 
If does not resolve to Grade 3 within 48 hours, permanently discontinue study agent.
 
If resolves to Grade 3 within 48 hours, then:
 
First Occurrence:
 
 Hold until resolution to ≤ grade 1. If resolved in ≤ 7 days, resume at pre-hold dose. If resolved in 8-14 days, resume study agent at 10 mg. If not resolved within 14 days, permanently discontinue study agent. 
Recurrence:
 
 Hold until resolution to ≤ grade 1. If resolved in ≤ 14 days, resume study agent at 10 mg. If not resolved within 14 days, permanently discontinue study agent. 
At 10 mg: Permanently discontinue study agent.

Vomiting or Nausea Grade 1	Maintain study agent.
Vomiting or Nausea Grade 2	Maintain study agent.
Vomiting or Nausea Grade 3	
At 20 mg:
 
Hold study agent and provide optimal supportive care/therapy.
 
First Occurrence:
 
 If resolves to ≤ grade 1 in ≤ 7 days, resume at pre-hold dose. If resolves to ≤ grade 1 in 8-14 days, resume study agent at 10 mg. If does not resolve within 14 days, permanently discontinue study agent. 
Recurrence:
 
 If resolves to ≤ grade 1 in ≤ 14 days, resume at 10 mg. If does not resolve within 14 days, permanently discontinue study agent. 
At 10 mg: Permanently discontinue study agent.

Vomiting Grade 4	
At 20 mg:
 
Hold study agent and provide optimal supportive care/therapy.
 
If does not resolve to Grade 3 within 48 hours, permanently discontinue study agent.
 
If resolves to Grade 3 within 48 hours, then:
 
First Occurrence:
 
 Hold until resolution to ≤ grade 1. If resolved in ≤ 7 days, resume at pre-hold dose. If resolved in 8-14 days, resume study agent at 10 mg. If not resolved within 14 days, permanently discontinue study agent. 
Recurrence:
 
 Hold until resolution to ≤ grade 1. If resolved in ≤ 14 days, resume study agent at 10 mg. If not resolved within 14 days, permanently discontinue study agent. 
At 10 mg: Permanently discontinue study agent.

Hepatic investigations	
ALT (SGPT) or AST (SGOT) ≤ 3.0 x ULN or TBili ≤ 1.5 x ULN	Maintain study agent.

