ALT (SGPT) or AST (SGOT) >3.0 - 5.0 x ULN or TBili >1.5 - ≥ 3.0 x ULN	
First Occurrence:
 
Hold until resolution to < 3.0 x ULN for ALT or AST or < 1.5 for TBili. Resume at pre-hold dose if resolved within 14 days. If does not resolve within 14 days, permanently discontinue study agent.
 
Recurrence:
 
Hold until resolution to < 3.0 x ULN for ALT or AST or <1.5 for TBili. Resume at 10 mg if resolved within 14 days. If does not resolve within 14 days, permanently discontinue study agent.

ALT (SGPT) or AST (SGOT) > 5.0 x ULN or TBili > 3.0 x ULN	Permanently discontinue study agent.
Electrolyte/metabolic toxicity	
Electrolyte/metabolic Grade 3	
Provide support care. Maintain study agent per investigator discretion.
 
If alteration persists despite aggressive replacement therapy, then dose reduce or permanently discontinue (per investigator discretion with PI consultation).

Electrolyte/metabolic Grade 4	
Provide support care. Maintain study agent per investigator discretion.
 
If resolves to Grade 1 or baseline within 48: for first event, maintain at pre-hold dose; for recurrent event, dose reduce or permanently discontinue (per investigator discretion with PI consultation).
 
If does not resolve to Grade 1 or baseline within 48 hours, permanently discontinue study agent.

Other unspecified Non-Hem toxicities considered related to leflunomide	
Grade 1	Maintain study agent.
Grade 2	Maintain study agent.
Grade 3	
First Occurrence:
 
Hold until resolution to ≤ Grade 2. Resume at pre-hold dose if resolved within 7 days. If does not resolve within 7 days, permanently discontinue study agent.
 
Recurrence:
 
Hold until resolution to ≤ Grade 1. Resume at 10 mg if resolved within 14 days. If does not resolve within 14 days, permanently discontinue study agent.

Grade 4	Permanently discontinue study agent.
Other unspecified Non-Hem Toxicities considered UNRELATED to study agent	
Other unspecified events of any grade considered unlikely to be related or not related to study agents.	Maintain treatment with study agents. Interruption of study agent or dose de-escalation is permitted if the investigator consults with the Principal Investigator to determine that this is in the best interest of the participant.

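### Table 7.1.1 prints an invalid bilirubin hold band, and its hepatic rows do not cover the Gilbert's patients whom inclusion criterion 10 admits

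*Combined protocol and SAP*

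**What the plan says.** Table 7.1.1 has three hepatic rows.

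- Maintain: "ALT (SGPT) or AST (SGOT) ≤ 3.0 x ULN or TBili ≤ 1.5 x ULN".
- Hold: "ALT (SGPT) or AST (SGOT) >3.0 - 5.0 x ULN or TBili >1.5 - ≥ 3.0 x ULN".
- Permanently discontinue: "ALT (SGPT) or AST (SGOT) > 5.0 x ULN or TBili > 3.0 x ULN".

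The restart rule in the hold row is "Hold until resolution to < 3.0 x ULN for ALT or AST or < 1.5 for TBili". For a first occurrence and for a recurrence alike, the row ends in permanent discontinuation if the values have not resolved within 14 days.

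Section 7.1.1 item d adds a general rule for holds due to drug-related toxicity: "if the participant does not meet criteria to resume treatment within 14 days, the participant must permanently discontinue study treatment". Item c defines baseline ("Baseline values are from the last values obtained prior to treatment"), but no hepatic row uses it. The Grade 4 electrolyte/metabolic row, by contrast, does accept a return to baseline.

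Inclusion criterion 10 in Section 3.1 sets total bilirubin at no more than 1.5 x ULN, "unless has Gilbert's disease". It gives no ceiling for those patients.

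**The concern.** These rows decide when leflunomide is held, restarted or stopped for abnormal liver tests. Section 6.1 lists hepatic failure and acute hepatic necrosis among the rare but possibly serious events, so the thresholds should be usable exactly as printed. One of them is not: its two limits point the same way.

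The second issue is a mismatch between entry and treatment rules. The protocol deliberately admits patients whose bilirubin is above 1.5 x ULN because of Gilbert's disease, then applies treatment rules under which that same stable value leads off treatment. The two defects are linked, because correcting the sign is what brings Gilbert's patients between 1.5 and 3.0 x ULN into the hold band.

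**Working it through.** The plan gives no figure to reproduce. The check sets the printed limits side by side and applies them to single values.

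**Inputs.** From Table 7.1.1: bilirubin limits of 1.5 and 3.0 x ULN, restart below 1.5, and a 14-day limit on the hold. From Section 3.1: the Gilbert's exemption in criterion 10. The bilirubin values below are illustrative.

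**Step 1: the bilirubin limits alone, with ALT and AST at 1 x ULN.** If both printed inequalities must hold, >1.5 and ≥ 3.0 reduce to ≥ 3.0. The other way to read the print is everything above 1.5 with no upper limit.

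| TBili (x ULN) | Printed, literal (≥ 3.0) | Printed, no upper limit | Corrected (>1.5 to ≤ 3.0) |
|---|---|---|---|
| 1.5 | maintain | maintain | maintain |
| 2.0 | no bilirubin limit met | hold | hold |
| 3.0 | hold | hold | hold |
| 3.2 | hold and discontinue | hold and discontinue | discontinue |

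On the literal reading, the only row that the patient at 2.0 x ULN satisfies is maintain, through the normal transaminases. Only the corrected band gives one action for each bilirubin value.

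**Step 2: the restart limit.** The transaminase limit carries the x ULN unit and the bilirubin limit does not. Every other bilirubin limit in these rows is a multiple of ULN, so < 1.5 x ULN is the evident meaning.

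**Step 3: Gilbert's patients on the corrected band.** Let b be a stable pre-treatment bilirubin in multiples of ULN, with normal transaminases.

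- b = 2.0: eligible under criterion 10. Since 2.0 > 1.5 and 2.0 ≤ 3.0, the hold row applies. Restart needs a value below 1.5; 2.0 does not meet it, so the row ends in permanent discontinuation after 14 days. The study calendar (Table 10.0) puts the first on-treatment chemistry panel at Cycle 1 Day 14 (±3 days), so discontinuation falls at about day 14 + 14 = 28, the end of the first of up to 13 cycles.
- b = 3.2: eligible on bilirubin, because the exemption has no ceiling. Since 3.2 > 3.0, the discontinue row is already met before the first dose.
- In general, any stable b from above 1.5 to 3.0 is held and then discontinued, and any b above 3.0 is discontinued at once. No patient who needs the exemption and whose bilirubin stays at its baseline can remain on treatment under the rows as intended.

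**The case against.** **The sign.** The text was machine-read from a PDF, and the ≥ may be a reading artefact. That is possible, and the source should be checked first. The neighbouring discontinue row fixes the intended limit in either case, so few investigators would be misled. This lowers the practical risk; it does not make the band valid if the source prints it this way.

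**Gilbert's disease.** The introduction to Table 7.1.1 speaks of toxicities on leflunomide, and item d of Section 7.1.1 is limited to related toxicities. A stable pre-existing bilirubin is neither. But the hepatic row states its own 14-day discontinuation with no relatedness condition, and the table's row for unrelated events covers only events not otherwise specified, whereas bilirubin has its own row. Exclusion criteria 9 and 11 would let an investigator decline a patient at 3.2 x ULN, but nothing requires it. The synopsis states the bilirubin limit without the exemption, but it is labelled abbreviated, and registration uses the Section 3.0 checklist, which contains it.

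**Stronger readings that the documents do not support.**

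- A reader might infer that the 'or' in the maintain row leaves the action open, for example that ALT 8 x ULN with normal bilirubin is both maintained and discontinued. The table pairs an event with an action, and 'or' lists events that share the action, as in its combined vomiting and nausea rows. A normal bilirubin does not cancel the ALT row.
- A reader might infer that restart is undecided when two tests are abnormal, for example ALT falling from 4 to 2.5 and bilirubin from 2 to 1.8 x ULN by day 14. The bilirubin of 1.8 is still inside the intended hold band, so resuming would meet the hold row again.
- A reader might take restart at '<' against maintain at '≤' for an error. Restart stricter than maintain is the table's pattern: Grade 3 neutropenia is maintained, yet restart after Grade 4 needs Grade 2 or better; Grade 2 diarrhea is maintained, yet restart after Grade 3 needs Grade 1 or better.

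**Conclusion.** The point holds for two defects: the bilirubin hold band is invalid as printed, and the hepatic rows give the wrong result for an eligible Gilbert's patient with a stable baseline value. Both should be fixed. The first is probably a one-character error whose intended value is clear. The second is a substantive conflict between Sections 3.1 and 7.1.2 that sensible reading of the table does not remove.

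The size is modest. The documents give no frequency of Gilbert's disease, and accrual is capped at 14, so the number of patients affected is unknown and may be none. Sample size and the primary analysis are not affected. The conclusion assumes that the source PDF prints the band as quoted (for the first defect), that ≤ 3.0 x ULN is the intended limit, and that the patient's bilirubin stays at its pre-treatment level (for the second).

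**What to change.** 1. Check the source PDF and print the bilirubin hold band as >1.5 to ≤ 3.0 x ULN. Write the bilirubin restart limit as < 1.5 x ULN, for first occurrence and recurrence.
2. Add one sentence: for patients enrolled under the Gilbert's exemption, the bilirubin hold, restart and discontinue limits are set relative to the patient's own pre-treatment bilirubin, using the baseline in Section 7.1.1 item c, with ALT and AST limits unchanged. The multiples are the sponsor's choice; the documents give none.
3. As low-cost clarification only: join the maintain conditions with 'and'; state in Section 7.1.1 that the most severe row met governs; and state that restart requires ALT < 3.0, AST < 3.0 and TBili < 1.5 x ULN. Keep '<' for restart.

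The cost is a wording change in a protocol amendment. No threshold changes for other patients. A baseline-relative rule needs no new test, because total bilirubin is already on the chemistry panel; a rule based on direct bilirubin would add a component that the panel does not list.

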- Prior diagnosis of rheumatoid arthritis
- Prior allogeneic transplant
- Acute active infection, known HIV, HBV, HCV infection
- Preexisting liver disease

- History of allergic reactions attributed to compounds of similar chemical or biologic composition to leflunomide or cholestyramine.
- Non-hematologic malignancy within the past 3 years aside from the following exceptions:
 - adequately treated basal cell or squamous cell skin cancer
 - carcinoma in situ of the cervix
 - prostate cancer < Gleason Grade 6 with a stable PSA
 - successfully treated in situ carcinoma of the breast

Investigational Product Dosage and Administration

Leflunomide will be administered orally at a dose of 20 mg/day following a loading dose of 100 mg/day for the first three days of administration.

Clinical Observations and Tests to be Performed

- Clinical observations will include tolerance as well as response to treatment.
- Baseline studies will include: history and physical, skin biopsies (the skin biopsy will be used for clinical assessment and leftover samples will be used for correlative laboratory studies), as well as a laboratory evaluation to include CBC with differential, comprehensive chemistry panel (to include LDH, magnesium, phosphorus and uric acid).
- Clinical observation of response will take place on day 1 of each 28-day cycle. Subjects will be evaluated through clinic visits and physical exams as well as laboratory tests to include CBC with differential, comprehensive chemistry panel. Blood tests will be performed at a minimum of every 28 days but may be done more frequently as clinically indicated.
- Skin biopsy will be performed at the baseline, after 1 month, 4 months of Leflunomide therapy and at end of therapy (if lesions are present), and at disease progression.
- Patients will undergo toxicity assessment every two weeks for the first three cycles following initiation with leflunomide and will undergo, at a minimum, monthly toxicity assessments thereafter.

TABLE OF CONTENTS

SECTION	PAGE
Protocol Team	2
Study Schema	3
Protocol Synopsis	4
Table of Contents	7
Abbreviations	9
1.0 Objectives	10
1.1 Primary Objective	10
○ To evaluate overall response rate of leflunomide treatment	10
1.2 Secondary Objectives	10
1.3 Exploratory Objectives	10
2.0 Background.....	10
2.1 Introduction/Rationale for Development	10
2.2 Leflunomide	10
2.3 Preclinical Studies of Leflunomide as an antineoplastic agent	11
2.4 Background for Correlative Studies	12

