5.2 Cycle Definition

The planned cycle length is 28 days. Leflunomide will be taken orally once daily. Missed or held doses will not be made up. The day count continues despite a hold in agent administration. Day 1 safety assessments must be reviewed prior to the initiation of the cycle. **For a cycle to commence, the participant must be actively taking study agent.** Windows for procedures are detailed in [Section 10.0](#).

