5.6 Duration of Therapy and Criteria for Removal from Protocol Therapy

Patients will receive study treatment for a maximum of 13 cycles until disease progression, unacceptable toxicity or other criteria for removal from study treatment are satisfied. Participants may be removed from treatment for any of the following reasons:

- Evidence of disease progression per mSWAT (see [Appendix C](#))
- Participant receives 13 cycles (~ 12 months of protocol therapy)
- Patient is deemed intolerant to study treatment because of toxicity, despite dose modification/delay
- Participant withdraws from the treatment phase of the study
- General or specific changes in the participant's condition, including non-compliance, which renders the participant unacceptable for further treatment in the opinion of the treating investigator.

Documentation of the reason for discontinuing therapy and the date effective should be made in the medical record and appropriate eCRF. The participant should then proceed to off-treatment procedures for safety monitoring, leflunomide elimination and follow-up procedures. The participant's status is to be modified in the OnCore system once the off-treatment period is completed. Alternative care options will be discussed with the participant.

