8.1.4 Pharmacology

Following oral administration, leflunomide is metabolized to an active metabolite teriflunomide (A77 1726) which is responsible for essentially all of its activity *in vivo*. Following oral administration, peak levels of the active metabolite occurred between 6 to 12 hours after dosing. Due to the very long half-life of teriflunomide (~2 weeks), a loading dose of 100 mg for 3 days was used in clinical studies to facilitate the rapid attainment of steady-state levels of teriflunomide. Without a loading dose, it is estimated that attainment of steady-state plasma concentrations would require nearly two months of dosing. Biliary recycling is a major contributor to the long elimination half-life of teriflunomide. The active metabolite of leflunomide is eliminated slowly from the plasma. Use of a drug elimination procedure (cholestyramine or activated charcoal) is used to reduce the drug concentration more rapidly after stopping leflunomide therapy.

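### Two rows of Table 7.1.1 permit repeated rechallenge at 10 mg, the lowest dose, where all eight hematologic and GI hold rows stop the drug

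*Combined protocol and SAP*

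**What the plan says.** Section 5.3.1 gives two maintenance doses: 20 mg/day, or 10 mg/day after a reduction for toxicity. Section 7.1.1 makes Table 7.1.1 the source of the modification rules. Its item (d) requires a permanent stop when a hold for related toxicity does not meet the criteria to resume within 14 days.

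Two rows of the table divide only into first occurrence and recurrence: the hepatic row for ALT/AST >3.0-5.0 x ULN (or the matching bilirubin band), and the related 'Other unspecified Non-Hem' Grade 3 row. A first event resumes at the dose held. For a recurrence, both rows say: "Resume at 10 mg if resolved within 14 days. If does not resolve within 14 days, permanently discontinue study agent".

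Above these tiers the rules are strict. For "ALT (SGPT) or AST (SGOT) > 5.0 x ULN or TBili > 3.0 x ULN" the drug stops permanently at any dose, and so it does for a related unspecified Grade 4 event.

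Section 5.6 adds the general limits. It says "Patients will receive study treatment for a maximum of 13 cycles", and the same sentence goes on to end treatment at progression, unacceptable toxicity or another removal criterion. The list that follows opens with "Participants may be removed from treatment for any of the following reasons" and includes "Patient is deemed intolerant to study treatment because of toxicity, despite dose modification/delay".

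**The concern.** The recurrence instruction reads as a dose reduction, and for a patient on 20 mg it is one. For a patient already on 10 mg it changes nothing, and the next recurrence meets the same instruction. A related toxicity that has come back at the lowest dose can therefore be rechallenged at that dose repeatedly, provided each episode resolves in time and stays below the permanent-stop severity.

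The stake is patient safety in the middle severity tier. Section 6.1 lists hepatitis, hepatic failure and acute hepatic necrosis as rare but possibly serious. The unspecified row is the catch-all for related toxicities without a row of their own, such as interstitial lung disease. A hold is also slow to act on a drug with a half-life of about 2 weeks (Section 8.1.4), and the cholestyramine washout in Section 5.5 is specified only after the decision to end treatment.

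**Working it through.** **1. Count of hold rows in Table 7.1.1.**

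- Hematologic rows that hold and may resume: febrile neutropenia G3, neutropenia G4, thrombocytopenia G3 with bleeding, thrombocytopenia G4 = 4.
- GI rows that hold and may resume: diarrhea G3, diarrhea G4, vomiting or nausea G3, vomiting G4 = 4.
- With a permanent stop at 10 mg: 4 + 4 = 8 of 8.
- Hepatic >3.0-5.0 x ULN and related unspecified G3, with a stop at 10 mg: 0 of 2.

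Febrile neutropenia G4 is an outright stop, so it is not a hold row. The electrolyte rows leave reduction or stopping largely to the investigator and are not counted.

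**2. The rules side by side** (dose on resuming, by time to resolution).

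| Row | First event at 20 mg | Recurrence at 20 mg | Event at 10 mg |
|---|---|---|---|
| Diarrhea G3; vomiting or nausea G3 | 20 mg if within 7 days; 10 mg if 8-14 days | 10 mg if within 14 days | Stop |
| Related unspecified G3 | 20 mg if within 7 days, otherwise stop | 10 mg if within 14 days | First: 10 mg if within 7 days. Recurrence: 10 mg if within 14 days |
| Hepatic >3.0-5.0 x ULN | 20 mg if within 14 days | 10 mg if within 14 days | First or recurrence: 10 mg if within 14 days |

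For events that each resolve within 7 days, the sequences are:

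- diarrhea or vomiting/nausea G3: 20 -> 20 -> 10 -> stop;
- related unspecified G3 and hepatic: 20 -> 20 -> 10 -> 10 -> 10, and so on.

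**3. Whether another rule closes the gap.** Section 7.1.1(d) limits the length of a hold, not the number of holds. Section 5.3.1 refers to Section 7.2 for toxicity modifications, but 7.2 concerns cholestyramine. The higher-severity stops do not reach a mid-tier event. Section 5.6 does reach it, through unacceptable toxicity and intolerance, but names no threshold for recurrence at 10 mg.

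**4. What a hold does to exposure.** Assume one compartment, a half-life of 14 days and 10 mg steady state = 1.

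- Patient already at 10 mg steady state, 14-day hold: level = 0.5. After resuming 10 mg, level = 1 - 0.5 x 0.5^(t/14): 0.75 at 14 days and 0.875 at 28 days. The level climbs back towards the one at which the event recurred.
- Patient just reduced from 20 mg steady state (level 2), 7-day hold: 2 x 0.5^(7/14) = 1.41. At 14 days after resuming at 10 mg: 1 + 0.41 x 0.5 = about 1.21. This patient is still above 10 mg steady state.

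The first result therefore applies only to a patient already at 10 mg steady state. In the second case, an early recurrence may reflect drug left over from 20 mg.

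**The case against.** The strongest reply is that the plan already ends treatment for unacceptable toxicity. The Section 5.6 sentence says so, the synopsis, Section 2.5 and the Table 10.0 footnotes repeat it, and the listed intolerance criterion describes a patient still in trouble after modification. This stands, and it rules out the reading that such a patient could never be taken off drug. What remains is that judgment decides, in two rows, what the table decides by rule in eight others.

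Second, the hepatic row is not a like-for-like comparator. It is a middle tier, and the table tolerates repeated events below its hold tiers elsewhere: neutropenia G3, thrombocytopenia G3 without bleeding and diarrhea G2 all continue drug however often they recur. This also stands, and it weakens the hepatic half of the point. It does not touch the unspecified G3 row, for which diarrhea G3 and vomiting/nausea G3 are direct comparators.

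Third, a mandatory stop could end treatment before 10 mg has had a fair test, because of carry-over from 20 mg. That is a true cost, but the eight other rows already accept it.

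Fourth, an instruction to resume at 10 mg may presume a patient on 20 mg. If so, the table says nothing about recurrence at 10 mg. On either reading no rule stops the drug.

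A reader might also try to count the resumptions possible within 13 cycles from the scheduled chemistry panels. The documents do not support a figure. Section 5.2 says "The day count continues despite a hold in agent administration", but it also lets a cycle start only if the participant is taking drug, so a Day 1 that falls in a hold shifts the later cycles.

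**Conclusion.** The point holds in a limited form. Two of the ten hold rows compared set no stop at 10 mg, and their wording permits same-dose rechallenge without a limit on repeats. The case is clear for the related unspecified Grade 3 row and weaker for the hepatic row.

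A reader might infer that the plan is lax on liver toxicity generally. It is not: the severe hepatic and unspecified tiers stop drug at once at any dose, whereas the diarrhea and vomiting Grade 4 rows allow some resumption from 20 mg. Nor is treatment open-ended, given the 13-cycle maximum and Section 5.6. Worsening or slow resolution also forces a stop, so harm is partly contained.

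The documents give no basis for estimating how often a patient would follow this path, and they do not say whether the difference between rows is deliberate. The row count rests on the table text alone; only the exposure figures need the one-compartment assumption. Sample size and the primary analysis are unaffected. This is a cheap improvement.

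**What to change.** In both rows, limit the recurrence instruction to patients on 20 mg at the time of the event, and add the line: *Recurrence of the same toxicity at 10 mg: permanently discontinue study agent.* Leave the first-occurrence text unchanged.

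The longest sequence for one toxicity starting at 20 mg becomes 20 -> 20 -> 10 -> stop. A patient reduced to 10 mg for a different toxicity keeps one resumption after a first event. The eight other rows do not allow that, so the fix narrows the inconsistency without removing it. If the sponsor wants further rechallenge at 10 mg, it should say so and set a limit.

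The cost is a protocol amendment to two table rows. A few patients may stop earlier, possibly including a responder with a mild reversible ALT/AST rise, or one whose early recurrence reflects carry-over from 20 mg.
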